### **6.3. Assessment of Participant Compliance with Investigational Agent**

Participants in this study will receive all doses of the assigned vaccine/placebo under direct observation.

### **6.4. Toxicity Prevention and Management**

Participants will receive investigational agents in facilities where the investigative team is familiar and practiced in the treatment of systemic allergic reactions. Standard therapeutic agents, oxygen, and equipment will be available on site to treat reactions. Refer to [Section 5.1.1 Allergic Reactions and Anaphylaxis](#).

### **6.5. Premature Discontinuation of Investigational Agent**

Vaccination will be prematurely discontinued for any participant for any of the following reasons:

- Participant has a CoFAR Grade 2 or higher systemic allergic reaction regardless of tryptase, or a CoFAR Grade 1 reaction with elevated tryptase [1.2 x baseline plus 2 ng/ml] that is at least possibly related to the first dose of the vaccine. If the systemic allergic reaction took place after the participant has left the vaccination clinic and no tryptase measurements are available, Grade 1 events will not constitute criteria for discontinuation, but counseling by a study physician will be required (see below).
- The investigator believes that it is no longer in the best interest of the participant to receive the second vaccination

In the above cases, the participant will be asked to return for his/her next in clinic study visit during which reactogenicity symptoms will be reviewed (electronic diary review or return and review of paper diary), adverse events (AEs) and concomitant medications will be recorded, and pre-vaccination biospecimens will be obtained per protocol.

Vaccination may be prematurely discontinued for any participant for any of the following reasons:

- If a participant has a Grade 1 (per [CoFAR Grading Scale](#)) systemic allergic reaction with no evidence of systemic mast cell activation to the first dose of either the Pfizer-BioNTech COVID-19 Vaccine or Moderna COVID-19 Vaccine, he/she will receive counseling by a study physician and will be allowed to receive a second dose if he/she so chooses.
- Because the placebo will consist of a normal saline injection, a reaction to placebo will not require termination from subsequent active vaccination, if the participant is willing to proceed following counseling.
- If a participant becomes pregnant between the first and second doses of vaccine, she will receive counseling by a study physician and will be allowed to receive a second dose if she so chooses.

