The first aim is independent of whether we can demonstrate a difference between the HA/MCD and the comparison groups. If the risk is low, this important information can be used to reassure highly allergic individuals that the vaccines are safe. Indeed, if no reactions are seen in the HA/MCD group, it would provide evidence that the reaction rate is less than approximately 1 in 275. Estimation of risk in the HA/MCD group, along with the corresponding confidence intervals, will be a key finding of this study regardless of the proportions of systemic allergic reactions observed. This information will be crucial to properly advise highly allergic individuals and those with poorly controlled allergic asthma or mast cell disorders, to maintain public trust in the safety of these vaccines, and to minimize vaccine hesitancy.

However, if the risk in the HA/MCD is demonstrable, we want to determine whether it is higher than that of the comparison population. We have set the 1% in the HA/MCD population as an arbitrary risk level for which we want to have the statistical power to compare the two populations. This protocol is powered to detect a difference of the

magnitude of 0.01 versus 0.0001 between the comparison and HA/MCD groups within each vaccine arm. If there are reactions in the HA/MCD population, but not enough to demonstrate a higher risk than in the other population, we will also have a corresponding confidence interval for the risk in the HA/MCD ruling out some particular risk level. We will also estimate the difference in vaccine reactions between the two populations.

In the event a significant number of immediate systemic allergic reactions to either or both vaccines are seen, a second focus of this study is to begin evaluating the mechanism(s) of allergic reactions to the COVID-19 vaccines, and to determine if specific risk factors can be identified by patient history or biomarker testing. The prospective design is important, because it will allow standardized collection of both clinical information and biospecimens before and after vaccination and, most importantly, at the time of immediate vaccine systemic allergic reactions, should such reactions occur. This information will be extremely helpful in improving the safety of this new and important vaccine platform.

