## Appendix 1. CoFAR Grading Scale for Systemic Allergic Reactions Version 3.0

Grade 1	Grade 2	Grade 3	Grade 4	Grade 5
Reaction involving one of the following organ systems in which the symptoms are mild:	Reaction involving two or more of the following organ systems in which the symptoms are mild:	Reaction involving one or more of the following organ systems:	Life-threatening reaction involving one or more of the following organ systems with or without other symptoms listed in Grades 1 to 3:	
Cutaneous Generalized pruritus, generalized urticaria, flushing, angioedema	Cutaneous Generalized pruritus, generalized urticaria, flushing, angioedema	Lower respiratory Throat tightness, wheezing, chest tightness, dyspnea, cough that respond to short-acting bronchodilator treatment (including IM epinephrine) with or without supplemental oxygen	Lower respiratory Throat tightness with stridor, wheezing, chest tightness, dyspnea, or cough associated with a requirement for supplemental oxygen and refractoriness to short-acting bronchodilator treatment (including IM epinephrine) 	
Upper respiratory Rhinitis, cough unrelated to laryngeal edema or bronchospasm	Upper respiratory Rhinitis, cough unrelated to laryngeal edema or bronchospasm			
Conjunctival Injection/redness, itching, tearing	Conjunctival Injection/redness, itching, tearing	GI Severe abdominal pain, more than two episodes of vomiting and/or diarrhea	OR  Respiratory compromise requiring mechanical support	
GI Nausea, abdominal pain (no change in activity level), single episode of vomiting and/or single episode of diarrhea	GI Nausea, abdominal pain (no change in activity level), single episode of vomiting, and/or single episode of diarrhea		Cardiovascular Reduced BP with associated symptoms of end-organ dysfunction (e.g., hypotonia [collapse], syncope) defined as: 
 
• Children: low systolic BP (age specific) or >30% decrease in systolic BP
 
• Adults: systolic BP of less than 90 mmHg or >30% decrease from baseline
 
	
	OR  Reaction involving at least one of the following organ systems in which the symptoms are moderate:			
	Cutaneous Generalized pruritus, generalized urticaria, flushing, angioedema			

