### Major and minor criteria used in the case definition of anaphylaxis

	Major Criteria	Minor Criteria
Dermatologic or mucosal	
 
• generalized urticaria (hives) or generalized erythema
 
• angioedema*, localized or generalized
 
• generalized pruritus with skin rash
 
	
 
• generalized pruritus without skin rash
 
• generalized prickle sensation
 
• localized injection site urticaria
 
• red and itchy eyes
 

Cardiovascular	
 
• measured hypotension
 
• clinical diagnosis of uncompensated shock, indicated by the combination of at least 3 of the following: 
 
• tachycardia
 
• capillary refill time <math>>3</math> s
 
• reduced central pulse volume
 
• decreased level of consciousness or loss of consciousness
 
 
 
	
 
• reduced peripheral circulation as indicated by the combination of at least 2 of 
 
• tachycardia and
 
• a capillary refill time of <math>>3</math> s without hypotension
 
• a decreased level of consciousness
 
 
 

Respiratory	
 
• bilateral wheeze (bronchospasm)
 
• stridor
 
• upper airway swelling (lip, tongue, throat, uvula, or larynx)
 
• respiratory distress—2 or more of the following: 
 
• tachypnoea
 
• increased use of accessory respiratory muscles (sternocleidomastoid, intercostals, etc.)
 
• recession
 
• cyanosis
 
• grunting
 
 
 
	
 
• persistent dry cough
 
• hoarse voice
 
• difficulty breathing without wheeze or stridor
 
• sensation of throat closure
 
• sneezing, rhinorrhea
 

Gastrointestinal		
 
• diarrhoea
 
• abdominal pain
 
• nausea
 
• vomiting
 

Laboratory		Mast cell tryptase elevation $>$ upper normal limit

\* Not hereditary angioedema

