7.2.1. Computation of the Primary Endpoints

The primary analyses will be conducted for participants enrolled under versions 1.0 through 4.0. For each population we will estimate the proportion of participants who experience a systemic allergic reaction (CoFAR Grade 2 and above regardless of tryptase, or CoFAR Grade 1 with elevated tryptase [1.2 x baseline plus 2 ng/ml]) within the 90-minute post-vaccination observation period to either dose of the Pfizer-BioNTech COVID-19 Vaccine and independently the Moderna COVID-19 Vaccine for both the HA/MCD and Comparison populations. These four proportions will be accompanied by their 95% exact (Clopper-Pearson) confidence intervals.

A systemic allergic reaction, categorized as yes or no, is defined as a participant having a reaction to either active dose 1 or active dose 2 (categorized as yes) or to neither active dose (categorized as no). Grade 1 systemic allergic reactions will only be categorized as yes if the tryptase is elevated as determined by the VCU lab. If the tryptase cannot be evaluated for a Grade 1 event (i.e. if missing a pre-treatment and/or post-treatment value), the study management team will determine the subjects categorization based on all available data for the subject.

Participants who do not have a systemic allergic reaction to the 1st active dose and missing data for their 2nd active dose will be removed from this analysis (complete case analysis).

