7.3. Secondary Endpoints

All secondary endpoints will be analyzed for participants enrolled under version 1.0 through 4.0. If sufficient numbers of children are enrolled, then adults 18 years of age and older will be also be analyzed separately from children.

7.3.1. Secondary Endpoint 1

Endpoint: The proportion of participants who experience a severe (Grade 3 or higher per [CoFAR Grading Scale for Systemic Allergic Reactions Version 3.0](#)) systemic allergic reactions within the 90-minute post-vaccination observation period to either dose of each vaccine.

Computation: A Grade 3 or higher systemic allergic reaction, categorized as yes or no, is defined as a participant having a Grade 3 or higher (per CoFAR Grading Scale V3.0) systemic allergic reaction to either active dose 1 or active dose 2 (categorized as yes) or to neither active dose (categorized as no).

Participants who do not have a systemic allergic reaction to the 1st active dose but missing data for their 2nd active dose will be removed from this analysis (complete case analysis).

Analysis: This analysis will be carried out as outlined in Section 7.2.2. A sensitivity analysis will be carried out as outlined in Section 7.2.3.

7.3.2. Secondary Endpoint 2

Endpoint: The proportion of participants who experience an anaphylactic reaction (Levels 1-3) per Brighton Collaboration Criteria within the 90-minute post-vaccination observation period to either dose of each vaccine.

Computation: An anaphylactic reaction (Levels 1-3) per Brighton Collaboration Criteria, categorized as yes or no, is defined as a participant having an anaphylactic reaction (Levels 1-3) per Brighton Collaboration Criteria to either active dose 1 or active dose 2 (categorized as yes) or to neither active dose (categorized as no).

Participants who do not have a systemic allergic reaction to the 1st active dose but missing data for their 2nd active dose will be removed from this analysis (complete case analysis).

Analysis: This analysis will be carried out as outlined in Section 7.2.2. A sensitivity analysis will be carried out as outlined in Section 7.2.3.

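### The removal rule in SAP 7.3.2 is worded for systemic allergic reactions, so on one reading an observed dose-1 Brighton anaphylaxis without dose 2 drops out of the anaphylaxis endpoint

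*Protocol*

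**What the plan says.** **The endpoint.** SAP 7.3.2 classes a participant as a Brighton case if a Level 1-3 reaction follows active dose 1 or active dose 2, with no reference to CoFAR grade. Protocol 1.1 gives the purpose: comparison with publications that use the Brighton criteria.

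**The removal rule.** SAP 7.3.2 then states: "Participants who do not have a systemic allergic reaction to the 1st active dose but missing data for their 2nd active dose will be removed". The same sentence stands in 7.3.1 and 7.3.5, whose endpoints are CoFAR grades.

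**The term it relies on.** SAP 7.2.1 gives the only general yes/no coding of a systemic allergic reaction, and adds: "Grade 1 systemic allergic reactions will only be categorized as yes if the tryptase is elevated". If tryptase cannot be evaluated for a Grade 1 event, the study management team decides the category.

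**When dose 2 is not given.** Protocol 6.5 ends vaccination if the following is at least possibly related to the first dose: "Participant has a CoFAR Grade 2 or higher systemic allergic reaction regardless of tryptase, or a CoFAR Grade 1 reaction with elevated tryptase". It also ends vaccination if "The investigator believes that it is no longer in the best interest of the participant to receive the second vaccination". After a Grade 1 reaction without evidence of mast cell activation, "he/she will receive counseling by a study physician and will be allowed to receive a second dose if he/she so chooses".

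**The two scales.** Protocol Appendix 1 places "Generalized pruritus, generalized urticaria, flushing, angioedema" in one cutaneous organ system. Protocol Appendix 2 lists "upper airway swelling (lip, tongue, throat, uvula, or larynx" as a major respiratory criterion, separate from the dermatologic ones.

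**The concern.** The condition for leaving the analysis is written in terms of one event, while the endpoint is another. That would be harmless if every Brighton Level 1-3 reaction also met the 7.2.1 definition, but the appendices do not make the scales nested.

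For an either-dose endpoint, the outcome is settled once dose 1 has produced an event. Dose-2 data cannot change a yes to a no, so no missing-data assumption justifies removing such a participant. Removing one can only lower the estimate. Protocol 14.4.3 expects these events to be extremely rare, so a single lost case could be the whole numerator.

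**Working it through.** **Step 1. Can a Brighton case be CoFAR Grade 1?** Take mild generalized urticaria with mild lip swelling, and tryptase below 1.2 x baseline + 2 ng/ml.

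| Scale | Classification | Result |
|---|---|---|
| CoFAR (Appendix 1) | Both signs cutaneous, one system, mild | Grade 1 |
| Brighton (Appendix 2) | Urticaria: major dermatologic; lip swelling: major respiratory | Level 1 |

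Mild generalized urticaria with a hoarse voice is Level 2 (major dermatologic plus minor respiratory). CoFAR does not list hoarseness, so this too is Grade 1. Nausea, injection-site urticaria and a hoarse voice give Level 3 (a minor respiratory criterion plus minor criteria from two other systems), while CoFAR sees only nausea. The overlap therefore exists at all three levels. Each example assumes that Brighton's sudden onset and rapid progression are met, that there is no clear alternative diagnosis, and that every CoFAR-listed sign is mild.

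**Step 2. What happens to such a dose-1 case?**

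| Dose 2 | Reading of *systemic allergic reaction* in 7.3.2 | Brighton analysis |
|---|---|---|
| Given, data available | Either | Kept, yes |
| Not given | Any CoFAR grade | Kept, yes |
| Not given | 7.2.1 definition (Grade 1 only with elevated tryptase) | Removed |

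Only the last row loses the case. Missing data for a dose 2 that was given would have the same effect.

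**Step 3. Reproduce the plan's precision figure.** Protocol 14.7 gives (0, 0.0036) for 0/1020. With no events, the Clopper-Pearson upper limit is 1 - 0.025^(1/n). For n = 1020 this is 1 - 0.025^(1/1020) = 0.00361, or 1 in 277. That agrees with the stated 0.0036 and with the claim to rule out 1 in 275.

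**Step 4. Effect of one lost case.** With x events in n, the upper limit is the 0.975 quantile of Beta(x + 1, n - x) and the lower limit is the 0.025 quantile of Beta(x, n - x + 1). The denominator is the planned 1020 HA/MCD participants per vaccine.

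| Assumed Brighton cases | Case kept | Case removed |
|---|---|---|
| 1, and it is the affected one | 1/1020 = 0.098% (0.0025% to 0.545%; upper limit 1 in 183) | 0/1019 = 0% (0 to 0.361%; upper limit 1 in 277) |
| 3, one of them affected | 3/1020 = 0.29% (0.06% to 0.86%) | 2/1019 = 0.20% (0.02% to 0.71%) |

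In the second row the estimate falls by about a third: 1 - (2/1019)/(3/1020) = 0.33.

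**Step 5. Does another planned analysis recover the case?** The tipping-point analysis in SAP 7.2.3, which 7.3.2 adopts, runs only when more than 5% miss the second active dose. One participant in 1020 is 0.1%. The by-dose rates in SAP 7.2.4 use the 7.2.1 definition, so they do not count the case either. It would remain in the adverse-event displays, but not in the Brighton estimate.

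**The case against.** The strongest reply is that the wider reading is the natural one. Protocol 3.1 and 6.5 call a Grade 1 event without mast cell activation a systemic allergic reaction, and SAP 7.2.1 itself speaks of Grade 1 systemic allergic reactions as a class wider than those coded yes. Where the SAP wants the narrow definition elsewhere (7.2.2, 7.2.4), it cites 7.2.1; section 7.3.2 does not. The per-protocol sample keeps people who miss dose 2 because of an allergic reaction, without a grade condition, and SAP 7.2.3 sets aside missingness due to allergic reaction. This stands as far as it goes: removal is one reading, not the settled meaning. But 7.3.2 neither names its analysis sample nor says which sense applies, so two programmers could report different counts.

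It is also fair that the example must satisfy several conditions at once, and that a moderate cutaneous sign would already be Grade 2.

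A reader might infer three stronger points, which the documents do not support:

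- *An anaphylaxis case goes on to dose 2 and is then lost.* A participant with dose-2 data is counted as a Brighton yes.
- *The dose-2 rule is contradictory or rests only on CoFAR grade and tryptase.* The synopsis, 3.1 and 6.5 apply the CoFAR and tryptase criterion consistently, none gives Brighton a stopping role, and 6.5 adds mandatory discontinuation on the investigator's judgment.
- *The primary endpoint is wrong to code such an event as no.* Protocol 1.1 declares CoFAR as primary and Brighton as a separate secondary endpoint. Its reassurance statement, "if no reactions are seen in the HA/MCD group, it would provide evidence that the reaction rate is less than approximately 1 in 275", can be read against the primary definition, with Brighton proportions reported alongside.

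**Conclusion.** The point holds as a gap in SAP 7.3.2. The rule can be read so that an observed dose-1 Brighton Level 1-3 event is removed from the endpoint that exists to count it, although its either-dose outcome is already known. This requires an event that is CoFAR Grade 1 without the tryptase rise, missing dose-2 data, and the 7.2.1 sense of the term.

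Under those assumptions, losing the only case in 1020 moves the upper limit from 0.545% to 0.361%, and the estimate from 0.098% to zero. The bias is downward only. The documents give no basis for how often this would occur, or for whether it would be commoner in HA/MCD than in the comparison group. Nothing here bears on the clinical rule for dose 2.

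**What to change.** Reword the removal sentence in SAP 7.3.2 so that it refers to the endpoint itself:

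- Any participant with an observed Brighton Level 1-3 event after either active dose stays in the analysis as a yes.
- A participant with missing dose-2 data is removed only if there was neither a Brighton Level 1-3 event nor a dose-1 reaction that ended vaccination.

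The cost is one reworded passage and the matching program line, using data already collected. The downside is that the reported upper limit may be slightly less favourable.

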## 7. Other Medications

### 7.1. Concomitant Medications

#### 7.1.1. Protocol-Mandated

Enrolled participants with existing epinephrine prescriptions will be encouraged to bring their epinephrine auto-injectors with them to each clinic visit. Expiration dates of prescribed epinephrine pens will be assessed during the collection of concomitant medications. If the epinephrine is expired, the study physician may offer to provide a prescription. If it is clear to the study team, that a participant does not have insurance coverage for epinephrine and/or cannot afford to purchase it, a study-provided pack of 2 pens may be dispensed. The decision of an individual to not carry epinephrine (for any reason) will not be exclusionary for study participation.

#### 7.1.2. Other Permitted Concomitant Medications

Other than the prohibited medications listed in [Section 7.3 Prohibited Medications](#), treatment with concomitant medications is permitted throughout study participation.

### 7.2. Prophylactic Medications

Female participants of child-bearing potential must use an effective method of contraception (e.g. total abstinence, oral contraceptives, IUDs, barrier method with spermicide, surgical sterilization or surgically sterilized partner, Depo-Provera, Norplant, NuvaRing, or hormonal implants) for the duration of study participation.

### 7.3. Prohibited Medications

The following medications are prohibited during participation in the study:

- Systemic immunomodulators including systemic steroids
- Biologic agents
- Any antibody agent for treatment or prevention of COVID-19
- Zileuton
- Vaccines administered outside of the study

If a participant takes a prohibited medication during the study, it should be recorded as a protocol deviation in the eCRF.

The study physician will determine whether the second vaccination should be administered or not and whether vaccination should be delayed based on the medication(s) the participant used.

### 7.4. Rescue Medications

The following medications may be used to treat an allergic reaction:

- Epinephrine 1 mg/mL; 0.15 – 0.5 mg IM
- $\beta$ -adrenergic agonist inhaler or nebulizer (e.g. albuterol)
- Antihistamines
- Steroids
- IV fluids
- Oxygen

Guidelines for the treatment of systemic allergic reactions are detailed in the MOP. Rescue medications should be recorded on the Concomitant Medications eCRF.

## 8. Study Procedures (Protocol versions 1.0 – 4.0)

A summary of complete study procedures is included in Tables A and B in [Appendix 3: Schedule of Events](#).

### 8.1. Recruitment & Pre-Screening (Day -14 to Day 0)

Potential study participants may be identified by medical chart review or from a response to a study advertisement, and initially contacted by a member of the study team in person or over the phone. During this initial contact, the potential participant will be provided information on the study and asked to provide verbal permission for pre-screening. If a participant provides verbal permission for pre-screening, they may be pre-screened over the phone using a standardized form to confirm eligibility. Eligible pre-screened individuals interested in participating in the study will be consented either remotely or during a clinic visit.

If it is possible to provide a physical copy of the consent and/or assent (if applicable) and verify who is consenting/assenting, remote consenting may be conducted. In the event of a remote consent, the participant will need to return the signed consent and/or assent (if applicable) to the clinic, prior to the conduct of any study procedures. The signed consent and/or assent may be returned via an approved electronic platform, in person, and/or by mail. The process for remote consenting will be further defined in the MOP.

In the event a site does not have the ability to conduct a remote consent and/or the participant or parent/legal guardian does not have access to the methods required for remote consent, an in-person clinic visit may be scheduled to complete the consenting process. Based upon the site's policies and vaccination schedules, this may be a separate clinic visit and/or combined with the Enrollment Visit.

